2. TRIAL OBJECTIVES AND ENDPOINTS

2.1 MAIN OBJECTIVES, PRIMARY AND SECONDARY ENDPOINTS

2.1.1 Main objectives

The main objective of Part 1 of this trial is to investigate the effect of co-administration of multiple doses of donepezil on the single-dose pharmacokinetics of BI 425809 in healthy subjects. In Part 2 the main objective is the investigation of the effect of co-administration of multiple doses of BI 425809 on the single-dose pharmacokinetics of donepezil in healthy subjects.

2.1.2 Primary endpoints

Part 1:

The following pharmacokinetic parameters will be determined for BI 425809:

- $AUC_{0-\infty}$ (area under the concentration-time curve of the analyte in plasma over the time interval from 0 extrapolated to infinity)
- C_{max} (maximum measured concentration of the analyte in plasma)

Part 2:

The following pharmacokinetic parameters will be determined for donepezil:

- $AUC_{0-\infty}$ (area under the concentration-time curve of the analyte in plasma over the time interval from 0 extrapolated to infinity)
- C_{max} (maximum measured concentration of the analyte in plasma)

2.1.3 Secondary endpoint

Part 1:

The following pharmacokinetic parameters will be determined for BI 425809:

- AUC_{0-tz} (area under the concentration-time curve of the analyte in plasma over the time interval from 0 to the last quantifiable data point)

Part 2:

The following pharmacokinetic parameters will be determined for donepezil:

- AUC_{0-tz} (area under the concentration-time curve of the analyte in plasma over the time interval from 0 to the last quantifiable data point)

2.2.2.2 Safety and tolerability

Safety and tolerability of BI 425809 will be assessed based on:

- Adverse events (including clinically relevant findings from the physical and neurological examination)
- Safety laboratory tests, including faecal occult blood test
- 12-lead ECG
- Visual tests
- Vital signs (blood pressure, pulse rate)
- Suicidality assessment (C-SSRS, only Part 2)

3. DESCRIPTION OF DESIGN AND TRIAL POPULATION

3.1 OVERALL TRIAL DESIGN AND PLAN

The study will consist of two parts and will be performed in healthy male and female subjects. Each subject does only participate in one part of the trial. Both parts are designed as open-label, two-treatment, two-period, one fixed sequence cross-over to investigate the effects of donepezil as perpetrator (Part 1) and as victim (Part 2) in relation to BI 425809.

Part 1 and part 2 are independent from each other as they investigate different pharmacokinetic objectives and endpoints of part 1 would not alter the rationale for part 2. Therefore completion of part 1 is not required to allow start of part 2. This of course does not apply for any safety issues as defined in the stopping criteria (ref [Section 3.3.4](#)).

Considering the well-known safety profiles of the selected dose of BI 425809 and donepezil, the unlikelihood of increased drug exposures due to a donepezil-BI 425809 interaction and the already implemented safety measures (ref [Section 1.4](#)) treatment of all subjects in one cohort per trial part, i.e. one cohort of 18 subjects in part 1 and one cohort of 14 subjects in part 2, respectively, is not considered to be an undue risk for enrolled subjects. However, treatment in cohorts for logistical reasons is possible. In this case, the cohorts should be of about the same size and be treated not too wide apart in terms of time for better comparability and reducing any possible factors influencing the readout.

In both parts there will be no washout period between treatments.

An overview of all relevant trial activities is provided in the [Flow Chart](#). For visit schedule and details of trial procedures at selected visits, refer to [Sections 6.1](#) and [6.2](#), respectively.

3.2 DISCUSSION OF TRIAL DESIGN, INCLUDING THE CHOICE OF CONTROL GROUP

Open-label design

Both parts (Part 1 and Part 2) are conducted open-label. Blinding is not possible because the treatments are distinguishable. The open-label treatment is not expected to bias results, since the study endpoints are derived from measurement of plasma concentrations of the analyte provided by a bioanalytical laboratory which is blinded to treatment allocation.

Fixed sequence design

A fixed sequence design was selected due to the long half-life of both, donepezil and BI 425809. The fixed-sequence design is not expected to lead to systematic errors in the estimation of the treatment effects, because the trial duration is short enough so that nonspecific time-effects are not expected.

In both part, dosing durations are long enough to achieve steady-state drug exposures of the perpetrator drugs (Part 1: donepezil, Part 2: BI 425809) reliably and to exclude any transient effects. Actually, dosing duration of BI 425809 with 10 days exceeds the time needed to

achieve steady state (after 6 days of dosing) to allow for maximum induction of CYP3A which is delayed compared to achievement of steady state.

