13. Colour discrimination, visual acuity testing, Amsler grid test: tests will be performed at screening, EOT and at any time visual adverse events are reported
14. All blood pressure measurements, as well as pulse rate and ECG will be measured after at least 5 minutes of rest in the supine position
15. Only urine drug screening and alcohol breath test and urine pregnancy testing in females
16. Bed rest (except going to the toilet)

* There is no wash-out period between Visit 2 and Visit 3. Day 1 of Visit 3 follows directly after day 8 of Visit 2 but these are different days

Part 2

Visit**	Day	Planned time (relative to first drug administration [h:min])	Approximate clock time of actual day [h:min]	Event and comment	Safety laboratory	PK _{plasma} (BI 425809)	PK _{plasma} Donepezil	Safety assessments	12-lead ECG ¹⁴	Vital signs (BP, PR) ¹⁴	Questioning for AEs and concomitant therapy ⁶	
1	-21 to -1	n.a.	n.a.	Screening ¹	X ⁵			X ^{9,10,13}	X	X		
2 (Treatment C)	-3 to -1	-24:00	n.a.	Ambulatory visit	X ¹²						X	
	-1	-12:00	20:00	Admission to trial site	X ¹⁵						X	
	1	-02:00	06:00			X ²	X ²	X ^{10,2}	X ²	X ²	X ^{2,7}	
		00:00	08:00	Drug administration, 10 mg donepezil								
		01:00	09:00				X					
		02:00	10:00	240 mL fluid intake			X					
		03:00	11:00				X					
		04:00	12:00	240 mL fluid intake, Lunch ³			X		X	X	X	
		06:00	14:00				X					
		08:00	16:00				X					
		10:00	18:00	Dinner ³			X					
	12:00	20:00				X		X	X	X		
	2	18:00	02:00				X					
		24:00	08:00			X	X		X	X	X	
	3	48:00	08:00			X	X				X	
	4	72:00	08:00			X	X					X
		72:30	08:30	Discharge ¹¹				X ¹⁰	X	X	X	
	5	96:00	08:00	Ambulatory visit			X		X	X	X	
6	120:00	08:00	Ambulatory visit			X					X	
7	144:00	08:00	Ambulatory visit			X					X	
8	168:00	08:00	Ambulatory visit			X					X	
9	192:00	08:00	Ambulatory visit			X					X	
10	216:00	08:00	Ambulatory visit		X	X	X ¹⁰	X	X	X		
11	240:00	08:00	Ambulatory visit			X					X	
12	264:00	08:00	Ambulatory visit			X					X	
13	288:00	08:00	Ambulatory visit			X					X	
14	312:00	08:00	Ambulatory visit			X					X	
15	336:00	08:00	Ambulatory visit		X	X					X	

Visit ^{3,4}	Day	Planned time (relative to first drug administration [h:min])	Approximate clock time of actual day [h:min]	Event and comment	Safety laboratory	PK _{plasma} (BI 425809)	PK _{plasma} Donepezil	Safety assessments	12-lead ECG ¹⁴	Vital signs (BP, PR) ¹⁴	Questioning for AEs and concomitant therapy ⁶	

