In human liver microsomes CYP-450 enzymes 1A2, 2C9, 2C19, 2D6 and 3A4 were inhibited by donepezil with IC_{50} values > 100 μ m. In addition, the mean k_i values for CYP-3A4 and CYP-2D6 were calculated to be 131 μ m and 47 μ m, respectively. Clinical studies have shown that the steady-state C_{max} for the 10 mg dose of donepezil is approximately 164 nm. Since it is anticipated that therapeutic concentrations of donepezil are more than 280-fold lower than the lowest k_i value obtained with CYP-2D6 and almost 800-fold lower than the k_i observed with CYP-3A4, it is expected that donepezil will not inhibit the metabolism of other drugs metabolized by these or any other CYP-450 isoenzymes [R18-3919].

Data from clinical trials in healthy volunteers indicate a good safety profile for daily doses up to 10 mg and an acceptable safety profile for a daily dose of 23 mg. This is in accordance with the sponsor's own experience of a trial in healthy volunteers that received multiple doses of donepezil [c09564954]

- A randomized, double-blind, multiple dose study was investigating the pharmacokinetic and pharmacodynamics profile of donepezil, clinical trials with healthy volunteers. Single daily doses of donepezil (5 and 10 mg) each evening were administered on 28 consecutive days.
8 subjects received 5 mg donepezil for 28 days, 8 subjects started with 5 mg donepezil and switched thereafter to a daily dose of 10 mg for the remaining 21 days. Donepezil was well tolerated by all subjects. The most frequently reported adverse events were headache, gastrointestinal upset, sleep disturbance and lethargy. All were transient, mild and resolved during continued treatment without the need for adjunctive therapy [[R05-0853](#)].
- An open-label, randomized, single-dose, two-period crossover study was investigating the bioequivalence of two extended-release tablets of donepezil 23 mg under fasting (n=74) and fed (n= 93) conditions.
In the fasting study, a total of 154 AEs were reported by 52 subjects. Of all AEs, two (increased neutrophil count and oral herpes) were unexpected and possibly related to the administration of the product. In the fed study, 81 subjects experienced a total of 305 AEs. Of all AEs, four (mydriasis, oral herpes, photophobia, and pupils unequal) were unexpected and possibly related to the administration of the (test or reference) products.

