No subject was withdrawn from the study for safety reasons. There were no deaths or serious adverse events reported. All of the observed AEs were considered to be resolved. Given this information, the study drugs appeared to be well-tolerated and there were no safety concerns observed [[R15-4356](#)].
- A study to investigate the pharmacokinetic drug-drug interaction following oral administration of BI 409306 and donepezil in 32 healthy male (n = 17) and female (n = 15) subjects. Part 1 of this trial was performed as a one fixed sequence, open-label trial, in which single doses of BI 409306 and multiple doses of donepezil (5 mg qd for 7 days followed by 10 mg qd for 14 days) were administered, Part 2 of this trial was a randomised, open-label, 2-way crossover design, in which single doses of donepezil and multiple doses of BI 409306 were given.
In Part 1 of the trial, i.e. after multiple doses of donepezil, 16 out of 18 subjects (88.9%) were reported with at least 1 AE that was assessed as drug-related. The most frequently reported drug-related AEs were dizziness and nausea (both 55.6% of subjects), followed by headache and fatigue (both 22.2%). Dizziness was only observed after administration of donepezil alone, whereas nausea and headache were observed after administration of donepezil alone and in combination with BI 409306. As expected visual brightness a known AE of BI 409306 was only observed after BI 409306 administration. Fatigue was observed in all 3 treatment phases.
All subjects completed the trial except for 1 subject in Part 1 who withdrew during the second treatment period (donepezil administration) because of AEs that were considered not to be drug-related (lower abdominal pain, haematochezia, and ruptured ovarian cyst) [[c09564954](#)].

According to [[R15-4794](#), [R18-3913](#)], the safety profile mainly results from the cholinergic activity of donepezil, resulting in

- Gastrointestinal symptoms (e.g. nausea, diarrhea, vomiting, abdominal pain, gastric and duodenal ulcers and gastrointestinal hemorrhage)
- Cardiac symptoms (e.g. syncope, bradycardia, sino-atrial block, atrioventricular block)
- Central-nervous symptoms (e.g. syncope, dizziness, insomnia, seizures, extrapyramidal symptoms and neuroleptic malignant syndrome)

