4.1.4 Drug assignment and administration of doses for each subject

This trial consists of two parts:

Part 1 is an open-label, two-treatment, two-period, one fixed sequence cross-over trial, in which all subjects will first receive BI 425809 (treatment A = Reference 1) alone and then again after multiple doses of donepezil (treatment B = Test 1).

The treatments to be evaluated in Part 1 are outlined in [Table 4.1.4: 1](#) below.

Table 4.1.4: 1 Part 1: Dosage and treatment schedule

Treatment	Substance	Formulation	Unit strength	Dosage	Total dose
A (Reference 1)	BI 425809	Tablet	25 mg	1 tablet (Day 1, Visit 2)	25 mg
B (Test 1)	Donepezil	Tablet	5 mg	1 tablet (Day 1-7, Visit 3) q.d. 2 tablets (Day 8-28, Visit 3) q.d.	245 mg
	BI 425809	Tablet	25 mg	1 tablet (Day 22, Visit 3)	25 mg

Part 2 has an open-label two-treatment, two-period, one fixed-sequence cross-over design. In Part 2 all subjects will first receive donepezil (treatment C = Reference 2) alone and then again after multiple doses of BI 425809 (treatment D = Test 2).

The treatments to be evaluated in Part 2 are outlined in [Table 4.1.4: 2](#) below.

Table 4.1.4: 2 Part 2: Dosage and treatment schedule

Treatment	Substance	Formulation	Unit strength	Dosage	Total dose
C (Reference 2)	Donepezil	Tablet	5 mg	2 tablets (Day 1, Visit 2)	10 mg
D (Test 2)	Donepezil	Tablet	5 mg	2 tablets (Day 10, Visit 3)	10 mg
	BI 425809	Tablet	25 mg	1 tablet (Days 1-24, Visit 3) q.d.	600 mg

Trial medication will be administered to fasted subjects only (for fasting periods please refer to [Section 4.2.2.2](#)). The investigator (or authorised designee) will administer the trial medication as an oral dose together with about 240 mL of water to subjects who are in a standing position. For drug administration, the so-called four-eye principle (two-person rule) should be applied. For this, one authorised employee of the trial site should witness the administration of trial medication, and – if applicable – its preparation (e.g. reconstitution), if correct dosage cannot be ensured otherwise.

In **Part 1**, subjects will be kept under close medical surveillance until 38 h following administration of BI 425809 on Day 1, Visit 2 and on Day 22 Visit 3. In addition subjects will remain under medical supervision for about 14 h following the first dose of donepezil on Day 1 Visit 3. This in-house surveillance period can be extended anytime if deemed necessary based on the medical judgement of the investigator.

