7.3.4 Safety analyses

Safety will be analysed based on the assessments described in [Section 2.2.2.2](#). All treated subjects (TS, refer to [Section 7.2](#)) will be included in the safety analysis. Safety analyses will be descriptive in nature and based on BI standards. No hypothesis testing is planned.

For all analyses, the treatment actually administered (= treatment at onset) to the subject will be used (any deviations from the randomised treatment will be discussed in the minutes of the Report Planning Meeting).

Treatments will be compared in a descriptive way. Tabulations of frequencies/proportions will be used to evaluate categorical (qualitative) data, and tabulations of descriptive statistics will be used to analyse continuous (quantitative) data.

Measurements (such as vital signs, or laboratory parameters) or AEs will be assigned to treatments (see [Section 4.1](#)) based on the actual treatment at the planned time of the measurement or on the recorded time of AE onset (concept of treatment emergent AEs). Therefore, measurements planned or AEs recorded prior to first intake of trial medication will be assigned to the screening period, those between first trial medication intake and end of REP (see [Section 1.2.3](#)) will be assigned to the treatment period. Events occurring after the REP but prior to next intake or end of trial termination date will be assigned to 'follow-up'. In case of two or more treatments, the follow-up will be summarized according to the previous treatment. These assignments including the corresponding time intervals will be defined in detail in the TSAP. Note that AEs occurring after the last per protocol contact but entered before final database lock will be reported to Pharmacovigilance only and will not be captured in the trial database.

Additionally, further treatment intervals (analysing treatments) may be defined in the TSAP in order to provide summary statistics for time intervals, such as combined treatments, on-treatment totals, or periods without treatment effects (such as screening and follow-up intervals).

Adverse events will be coded using the Medical Dictionary for Regulatory Activities (MedDRA). Frequency, severity, and causal relationship of AEs will be tabulated by treatment, system organ class, and preferred term. SAEs, AESIs (see [Section 5.2.7.1](#)), and other significant AEs (according to ICH E3) will be listed separately.

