The frequency of subjects with AEs will be summarised by treatment, primary SOC and preferred term. AEs which were considered by the investigator to be drug related will be summarised separately. Separate tables will also be provided for subjects with SAEs, subjects with AESIs and subjects with other significant AEs (according to ICH E3 (8)). AEs will also be summarized by maximum intensity.

The SOC and preferred terms within SOC will be sorted by descending frequency over all treatment groups.

For disclosure of AE data on ClinicalTrials.gov, the frequency of subjects with non-serious AEs occurring with an incidence of greater than 5 % (in preferred terms) will be summarised by treatment, primary SOC and preferred term. The frequency of subjects with SAEs will also be summarised.

For disclosure of AE data in the EudraCT register, the frequency of AEs, the frequency of non-serious AEs with an incidence of greater than 5 % (in preferred terms) and the frequency of SAEs will be summarized.

For support of lay summaries, the frequency of subjects with drug-related SAEs will be summarized by treatment, primary SOC and preferred term.

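### The Part 1 adverse-event columns mix donepezil titration into the comparison of donepezil alone with donepezil plus BI 425809, and the bias can run either way

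*Protocol*

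**What the plan says.** **Design rationale (Protocol 3.2).** On the fixed sequence: "The fixed-sequence design is not expected to lead to systematic errors in the estimation of the treatment effects".

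**Dosing (Protocol 4.1.4, Part 1).** Donepezil: "1 tablet (Day 1-7, Visit 3) q.d. 2 tablets (Day 8-28, Visit 3) q.d". The second BI 425809 dose: "1 tablet (Day 22, Visit 3". The Flow Chart footnote on wash-out says that "Day 1 of Visit 3 follows directly after day 8 of Visit 2 but these are different days", so donepezil starts 8 days after the first BI 425809 dose.

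**Safety columns (SAP 6.1, Table 6.1: 3).** The residual effect period is 11 days for BI 425809 and 15 days for donepezil.
- *Don part 1* has two stretches. One runs from 11 days after the first BI 425809 dose to the second BI 425809 dose. The other runs from 11 days after the second BI 425809 dose to 15 days after the last donepezil dose, or to trial termination if earlier.
- *Don + BI part 1* also has two stretches. One runs from the first donepezil dose to 11 days after the first BI 425809 dose. The other covers the 11 days after the second BI 425809 dose.

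**Use of the columns.** Protocol 7.3.4: "Treatments will be compared in a descriptive way". SAP 7.8.1: "The frequency of subjects with AEs will be summarised by treatment, primary SOC and preferred term". The unit is the subject with an AE, and no adjustment for time at risk is described. Protocol 7.3.4 lets the SAP define further treatment intervals; SAP 6.1 adds only totals.

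**Background (Protocol 1.2.2 and 4.1.2).** Up-titration is used for tolerability. Of AEs in a 28-day donepezil study: "All were transient, mild and resolved during continued treatment without the need for adjunctive therapy". Of an earlier interaction trial with the same step from 5 mg to 10 mg: "Dizziness was only observed after administration of donepezil alone".

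**The concern.** The sequence is fixed, so whatever changes with time on donepezil also changes between the columns. The protocol's own background makes it plausible that donepezil AEs depend on time since the start and since the dose increase. The SAP splits the titration between the two columns: the first three days go to the combination, while the rest of the 5 mg days and the step-up go to donepezil alone. A difference between the columns therefore cannot be read as the effect of adding BI 425809.

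Protocol 7.1 makes safety and tolerability a further objective, and the synopsis says that the interaction must be studied before concomitant use is allowed in Phase 3. Dizziness and headache are reported for both drugs (Protocol 1.2.2 and 1.4), so the confounding touches events of interest.

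**Working it through.** **1. Reproduce the SAP's planned durations.** Count in days from the first BI 425809 dose (day 0, 18:00). First donepezil dose: 8. Step to 10 mg: 8 + 7 = 15. Second BI 425809 dose: 8 + 21 = 29. Last donepezil dose: 8 + 27 = 35.
- BI part 1: 8 − 0 = 8 days.
- Don part 1: (29 − 11) + [(35 + 15) − (29 + 11)] = 18 + 10 = 28 days.
- Don + BI part 1: (11 − 8) + 11 = 14 days.

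All three match SAP 6.1 (8, 28 and 14 days).

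**2. What each column holds, in Visit 3 days.**

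| | Don part 1 | Don + BI part 1 |
|---|---|---|
| 5 mg doses | Days 4–7 (4 doses) | Days 1–3 (3 doses, start of donepezil) |
| Step to 10 mg | Day 8 | none |
| 10 mg doses | Days 8–21 (14 doses) | Days 22–28 (7 doses) |
| Other time | Days 33–43 (10 days, from 5 days after the last donepezil dose) | about 4 days after the last donepezil dosing interval |
| Total | 28 days | 14 days |

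**3. Length alone.** With a constant daily onset rate r (an assumption), the expected share of subjects with an AE is 1 − exp(−r × days). For r = 0.01: 24% over 28 days against 13% over 14. For r = 0.03: 57% against 34%. Neither involves an effect of BI 425809.

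**4. Titration, illustrated.** The documents give no AE onset times, so these rates are assumptions: background 0.01 per day during donepezil dosing and 0.005 afterwards; a peak, where present, of 0.15 per day for 3 days; a BI 425809 effect, where present, of +0.10 per day for 3 days from Day 22. Share = 1 − exp(−sum of daily rates).

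| Scenario | Sum, Don | Sum, Don + BI | Shares |
|---|---|---|---|
| Step-up peak, real BI effect | 4×0.01 + 3×0.15 + 11×0.01 + 10×0.005 = 0.65 | 3×0.01 + 3×0.11 + 4×0.01 + 4×0.005 = 0.42 | 48% vs 34%: effect hidden |
| Start peak, no BI effect | 18×0.01 + 10×0.005 = 0.23 | 3×0.15 + 7×0.01 + 4×0.005 = 0.54 | 21% vs 42%: false effect |
| Both peaks, no BI effect | 0.65 | 0.54 | 48% vs 42% |
| Both peaks, real BI effect | 0.65 | 3×0.15 + 3×0.11 + 4×0.01 + 4×0.005 = 0.84 | 48% vs 57% |

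**5. Rates per day at risk do not cure this.** With a step-up peak and no BI effect, the daily rates are 0.65/28 = 0.023 and (10×0.01 + 4×0.005)/14 = 0.12/14 = 0.009. With a start peak and no BI effect they are 0.23/28 = 0.008 and 0.54/14 = 0.039.

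**6. Matched windows.** Day 15 18:00 to Day 22 18:00 holds the doses of Days 15–21; Day 22 18:00 to Day 29 18:00 holds those of Days 22–28. Each has seven 10 mg doses. Under the same assumptions the first window gives 7×0.01 = 0.07, or 7%. The second gives 7% without a BI effect and 3×0.11 + 4×0.01 = 0.37, or 31%, with one. This holds in all four scenarios.

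**The case against.** The endpoints are pharmacokinetic, and safety is descriptive with no test. AE onset times are recorded and individual data are listed, so with 18 subjects a careful reader can place events relative to Days 8 and 22. The evidence for time dependence is thin: the earlier interaction trial used a different compound, and the protocol gives no onset days. Nausea, as frequent there as dizziness (55.6%), and headache occurred both on donepezil alone and in combination; fatigue occurred in all phases. This limits how much can be claimed about size. It does not rescue the tabulated comparison, which listings leave uncorrected.

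Two stronger readings are tempting, and the documents support neither.
- **A reader might infer that the bias can only hide an effect of BI 425809**, and carry the earlier trial's dizziness figure (10/18 = 55.6%) over as 55.6% on donepezil alone against 0% in combination. That needs onsets on Visit 3 Day 4 or later. If the same events began on Days 1–3, SAP Table 6.1: 3 would show 0% against 55.6%.
- **A reader might infer that Section 3.2 is wrong for safety.** Its sentence goes on to nonspecific time effects in a short trial, and the preceding paragraph concerns endpoints from plasma concentrations. Titration is a drug-specific effect, and the section makes no claim about AEs.

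**Conclusion.** The concern holds as a two-directional confounding built into SAP Table 6.1: 3. The composition of the columns is certain at nominal dosing times, provided that the end-of-trial visit (Days 44–49) does not cut the phases short. Whether donepezil AEs cluster at the start or after the step-up is plausible from Protocol 1.2.2 and 4.1.2 but not quantified there, so neither the size nor the net direction of the bias can be stated. The percentages in the working show only that masking and a false signal are both possible.

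The primary and secondary pharmacokinetic analyses are not affected. This should be changed because the correction is cheap and the Part 1 AE table is otherwise hard to interpret.

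**What to change.** In SAP 6.1 and 7.8.1, add a supplementary within-subject descriptive AE table for Part 1, assigned by AE onset:
- Visit 3 Day 15 18:00 to Day 22 18:00: donepezil 10 mg alone.
- Visit 3 Day 22 18:00 to Day 29 18:00: donepezil 10 mg with BI 425809.

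Show Days 1–3, Days 4–7 and the first week on 10 mg (Days 8–14) separately. Keep the existing tables, and say there that the first three donepezil days sit in the combination column.

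State the limits with the table. The second window covers 7 of the 11 residual-effect days of BI 425809. Observation is closer during the in-house stay on Days 22–24, so detection may be higher; AEs are asked about at least daily in both windows. The order is still fixed, and the comparison assumes that titration-related AEs have largely settled by Day 15.

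The cost is SAP wording and one table from data already collected, within what Protocol 7.3.4 allows. Dosing, visits and Protocol Section 3.2 need no change.
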